### **11.2. Concomitant Interventions**

All concomitant medications received by a subject during participation in the study will be recorded on the appropriate source documents.

#### **11.2.1. Required Concomitant Medications/Interventions**

No concomitant medications or interventions are required per protocol.

---

### **11.2.2. Prohibited Medications/Interventions**

Concomitant medications and interventions will be reviewed at screening. The investigator may choose to exclude a subject from participation if a concomitant medication or intervention is judged likely to interfere with the study objectives or to affect the subject's safety.

The following drugs are known to interact with Metformin tablets (US Package Insert; revision 05/2018) and should not be administered with Metformin:

- Agents that may increase Metformin blood concentration;
- Agents that may decrease Metformin plasma concentrations;
- Agents that may increase the risk of lactic acidosis; Carbonic anhydrase inhibitors may increase risk of lactic acidosis.
- Agents that may impact glucose control and cause hyper or hypo glycemia; Taking Metformin with other drugs that lower blood sugar can raise your risk of hypoglycemia (low blood sugar).
- Potentially hepatotoxic drugs: (e.g., allopurinol, methyldopa, sulfasalazine)
- Drugs that reduce metformin clearance (such as ranolazine, vandetanib, dolutegravir, and cimetidine) may increase the accumulation of metformin.
- Medications that interact with Metformin include digoxin, cimetidine, furosemide, nifedipine, amiloride, ranitidine, triamterene, morphine, quinidine, vancomycin, trimethoprim and procainamide.
- Alcohol can potentiate the effect of metformin on lactate metabolism and should not be used in excess while taking Metformin.

### **11.3. Subject Compliance**

Subject compliance will be assessed at all visits with direct and open questioning about compliance and adverse events. All returned medication will be counted. Greater than 10% noncompliance will prompt re-education of subject by the investigator on the importance of medication compliance.

---

## 12. STUDY PROCEDURES

### 12.1. Schedule of Activities

The schedule of study activities is presented in Table 3.

Timeline:

---

**Table 3. Schedule of Activities:**

Evaluation	Recruit & Screen	Visit 1	Visit 1	Visit 2	Visit 3	Phone Call	Visit 4	Visit 4	Phone Call	Phone Call
		Day 1	Day 2	6 weeks	12 weeks	18 Weeks	Day 1 24 weeks	Day 2 24 weeks	36 Weeks	52 weeks
		PM	AM	(42 days)	(84 days)	(126 days)	(168 days)	(168 days)	(252 days)	(365 days)
Informed Consent	X									
Inclusion/Exclusion Review	X									
Documentation of Disease	X									
Record/Review Concomitant Medications	X		X	X	X	X	X		X	
Medical History/Demographics	X		X			X				X
Vital Signs/Height and Weight	X		X	X	X		X			
Comprehensive Physical and Neurological Exams	X				X		X			
Brief Physical and Neurological Exam			X	X						
C9+ and RAN protein blood draw	X		X	X	X		X			
Clinical Labs for safety (hematology, chemistry, liver function and urinalysis)	X		X	X	X		X			
Urine Pregnancy Test (females of childbearing potential)	X		X	X	X		X			
Lumbar Puncture (for RAN proteins and biomarkers)			X	X	X		X			
MRI/DTI imaging			X					X		
VFSS Penetration-Aspiration Scale		X			X			X		
Functional Oral Intake Scale (FOIS)		X			X	X		X	X	X
ALS Functional Rating Scale – Revised (ALSFRS-R)	X		X	X	X	X	X		X	X
Eating Assessment Tool-10 (EAT-10)		X			X	X		X	X	X
Forced Vital Capacity (FVC)		X			X			X		
Peak Cough Flow		X			X			X		
Body Mass Index		X			X			X		
BDI-FastScreen	X			X	X		X			
Adverse Event			X	X	X	X	X		X	X
Dispense Study Drug			X	X	X					

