## Experimental Design

This is a single-center, open label safety and tolerability trial. Approximately sixteen (16) individuals with C9orf72 amyotrophic lateral sclerosis (ALS) will be enrolled. Subjects will be screened to determine eligibility according to the specified inclusion/exclusion criteria. Following informed consent, screening, and enrollment, during study visit 1, subjects will undergo clinical examinations and questionnaires including the validated amyotrophic lateral sclerosis functional rating scale-revised (ALSFRS-R). Subjects will have blood work performed to monitor clinical safety, RAN proteins and biomarker analyses. Lumbar punctures will be performed to allow measurements of RAN protein levels in the cerebrospinal fluid (CSF) and for molecular and biomarker analyses. MRI/DTI imaging will be obtained at the beginning of the study and at the end of the drug treatment phase. Subjects will return on Day 1 for swallowing and respiratory evaluation. The subjects will then be given a first dose of Metformin (with escalating dose of the drug. The initial dose during week one will begin at 500mg/day, in the following weeks this will increase to 1000 mg/day (week two), 1500 mg/day (week three) and 2000mg per day (weeks 4 to 24). The subjects will begin by taking the first dose in the morning during week one and then morning and evening doses in weeks 2-24 with an interim assessment at days 42, 84 and final evaluation at 168 days (+/- ~7) to assess the safety and tolerability of Metformin.

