**CONFIDENTIAL INFORMATION**

The information in this study protocol is confidential. Any disclosure, copying or distribution of the information contained within is strictly prohibited without written consent from University of Florida.

Assessments

[name]:

- Disease Documentation
- Comprehensive/brief physical exam
- Comprehensive/brief neurologic exam
- ALS Functional Rating Scale – Revised (ALSFRS-R)
- BDI-Fast Screen
- Eating Assessment Tool-10 (EAT-10)
- Functional Oral Intake Scale (FOIS)
- Forced Vital Capacity (FVC)
- Peak Cough Flow
- Body Mass Index
- Adverse events
- Clinical laboratory assessment, blood and urine
- Lumbar puncture for CSF collection (20 ml volume on each study visit)
- Vital signs/height and weight
- Medical history
- Concomitant medication
- Inclusion/exclusion criteria

[name]:

- MRI and DTI imaging of corticolumbar and corticobulbar tracts

[name], M.S., CCC-SLP, BCS-S:

- Videofluoroscopic Swallow Study (VFSS)

---

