### **12.2.2. On-Study/On-Intervention Evaluations/Procedures**

#### **12.2.2.1. Baseline, Visit 1, Day 1 pm and Visit 1, Day 2 am:**

The baseline visit (Visit 1, Day 1 pm and Visit 1, Day 2 am), will cover 2 days and include the first dose of study drug, and study drug dispensing. It will be scheduled within 14 to 28 days after the screening visit. At this visit inclusion/exclusion criteria and concomitant medications will be reviewed. Vital signs, brief physical and neurologic examination, as well as study questionnaires and testing will be performed as noted in the schedule of activities. To lessen travel for participants during the COVID-19 pandemic, and after the pandemic, the Visit 1, Day 1 and Visit 1, Day 2 may take place in the same week as the Screening visit. If these visits are scheduled to take place in the same week, the \*clinical labs for safety and \*blood draw for C9+ and RAN proteins, and \*urine pregnancy test, will not be repeated.

The following documentation and procedures will be performed at Baseline (Visit 1, Day 1):

---

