#### **CONFIDENTIAL INFORMATION**

The information in this study protocol is confidential. Any disclosure, copying or distribution of the information contained within is strictly prohibited without written consent from University of Florida.

- FOIS
- BDI-Fast Screen (BDI-FS)
- VFSS – Penetration Aspiration Scale
- EAT – 10
- Forced Vital capacity (FVC)
- Peak Cough Flow
- Body Mass Index

The following documentation and procedures will be performed at Baseline (Visit 1, Day 2):

- Adverse event review
- Inclusion/exclusion assessment
- Record/review Concomitant medications
- Medical history
- Vital signs; weight and height
- Brief physical exam
- Brief neurologic exam
- Clinical labs for safety (hematology, chemistry, liver functions, and urinalysis)
- Blood draw for C9+ and RAN proteins
- Lumbar puncture for RAN proteins and biomarkers
- Urine Pregnancy Test (females of childbearing potential)
- MRI/DTI imaging
- ALSFRS-R
- Dispense study drug

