#### **12.2.2.5. Study Visit 4, Week 24 Day 1 or Day 2:**

All subjects will return at week 24 for a two-day end of study evaluation. The visit window is to be scheduled at 24 weeks (168 days) plus or minus 3 days. Participants will be seen for assessment of any adverse events, and concomitant medications. Study drug accountability and compliance will be assessed. Vital signs, physical and neurologic examination, as well as study questionnaires and testing will be performed as noted in the schedule of activities.

The following documentation and procedures will be performed at Visit 4, Week 24, on Day 1 or Day 2:

- Adverse events
- Record/review concomitant medications
- Vital signs, weight and height
- ALSFRS-R
- Comprehensive physical exam
- Comprehensive neurologic exam
- Clinical labs for safety (hematology, chemistry, liver functions, and urinalysis) – Due to the COVID-19 Pandemic, and only for the participants currently enrolled (3) in this study, the clinical labs for safety will be drawn at a local lab or physician's office and will be shipped as needed. If there is any charge for the draw the participant may either pay the invoice and be reimbursed or have the lab contact the study team in the ICF to pay the invoice directly. This modification to the protocol is to prevent potential exposure to COVID-19 by minimizing participant travel to our site.
- Blood draw for C9+ and RAN proteins – Due to the COVID-19 Pandemic, and only for the participants currently enrolled (3) in this study, additional blood samples will be collected and will be shipped to the [name] Lab for analysis. The kits, drawing instructions, and shipping documents will be sent to the physician or the participant to complete this procedure. If there is a charge for the blood draw the participant may either pay the invoice and be reimbursed or have the lab contact the study team in the ICF to pay the invoice directly. This modification to the protocol is to prevent potential exposure to COVID-19 by minimizing participant travel to our site.
- Urine Pregnancy Test (females of childbearing potential)
- COVID-19 nasal collection and testing may take place at this visit if travel time allows for the participant - Due to COVID-19 Pandemic, nasal collection and testing of the participants has been implemented to determine if the participant is COVID

---

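### Table 3 puts swallowing, breathing and cough tests before the lumbar puncture at baseline but the day after it at Week 24, and no rule fixes the order

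*Combined protocol and SAP*

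**What the plan says.** Table 3 (section 12.1) gives two columns each to Visit 1 and Visit 4. The puncture row, "Lumbar Puncture (for RAN proteins and biomarkers", is marked at Visit 1 Day 2 (AM), Visit 2, Visit 3 and Visit 4 Day 1. The row "VFSS Penetration-Aspiration Scale" is marked at Visit 1 Day 1 (PM), Visit 3 and Visit 4 Day 2. FVC and peak cough flow carry the same marks. FOIS and EAT-10 do too, with additional telephone contacts. MRI/DTI is marked at Visit 1 Day 2 and Visit 4 Day 2.

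Section 12.2.2.1 repeats the baseline split in two lists, with these tests under Day 1 and the puncture and MRI under Day 2. Section 12.2.2.5 says that Week 24 testing follows the schedule of activities, but its single list opens with "The following documentation and procedures will be performed at Visit 4, Week 24, on Day 1 or Day 2". Section 12.2.2.3 lists the puncture and the tests for Week 12 without an order.

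The synopsis gives the collection as "Lumbar puncture for CSF collection (20 ml volume on each study visit" and closes the parenthesis there. After describing the puncture and imaging, its Experimental Design paragraph continues: "Subjects will return on Day 1 for swallowing and respiratory evaluation. The subjects will then be given a first dose of Metformin".

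The outcome list after Table 3 names PAS, DIGEST, FVC, cough flow and MRI/DTI as secondary outcomes. Section 15.3 lists impact on swallowing, respiratory testing and neuroimaging. Section 12.3.9 plans to compare DIGEST within individuals across Visits 1, 3 and 4.

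**The concern.** In a single-arm study the only contrast is each subject's later value against his or her own baseline. That contrast is clean only if the tests are done under the same conditions each time. Here one condition differs systematically as scheduled: no study puncture precedes the baseline tests, while a 20 ml puncture precedes the Week 24 tests by a day.

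FVC and peak cough flow depend on effort, and section 12.3.9.1 has subjects cough as hard as they can. If headache, back pain or fatigue after the puncture lowers performance in some subjects, the loss appears at the on-drug time point only. It could then be read as decline on metformin, or could mask a benefit. Blinded rating of the swallow recordings protects against rater bias. It does not correct for a difference in the subject's condition on the day.

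**Working it through.** The plan states no figure on this point, so the check is a comparison of the schedule rows, followed by an illustration on assumed inputs.

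**Step 1. Order of tests and puncture by visit.**

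| Visit | Puncture | VFSS, FVC, cough flow, FOIS, EAT-10 | MRI/DTI | ALSFRS-R |
|---|---|---|---|---|
| Visit 1 (Table 3; 12.2.2.1 agrees) | Day 2 AM | Day 1 PM, before | Day 2, order not stated | Day 2, puncture day |
| Visit 3 (Table 3; 12.2.2.3) | Same visit | Same visit, order not stated | Not done | Same visit |
| Visit 4 (Table 3) | Day 1 | Day 2, the day after | Day 2, the day after | Day 1, puncture day |
| Visit 4 (12.2.2.5) | Either day | Either day | Either day | Either day |

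Table 3 reverses the order of tests and puncture between baseline and Week 24. The baseline half is confirmed by the text. The Week 24 day split rests on Table 3 alone. ALSFRS-R falls on the puncture day at both ends of Table 3, so it has no such reversal.

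**Step 2. Is the order standardised elsewhere?** No. No section sets an interval or sequence between puncture and testing. Whether the Week 24 tests follow Table 3 or the freer wording of 12.2.2.5, they are not matched to baseline: under the table the order is reversed, and under the text it can vary between subjects.

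**Step 3. Who is exposed?** Not necessarily everyone. Sections 12.2.2.5 and 12.3.8 allow the 3 participants enrolled when that provision was written to have the Week 24 puncture near home. The synopsis (Interventions) allows drug to continue to Week 36 so that this can be arranged. That leaves 16 - 3 = 13 subjects on the standard schedule, and fewer exposed if 12.2.2.5 is used to test before the puncture.

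**Step 4. Possible size.** The documents give no frequency, duration or functional effect of puncture after-effects. All of the following inputs are assumptions. Let *f* be the share of subjects tested the day after a puncture, *p* the share of those with after-effects, and *d* the loss in points (for example, % predicted FVC) in those affected. Then

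shift in mean change = f × p × d.

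With f = 1 (Table 3 followed for all):

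- p = 0.10, d = 2: 0.10 × 2 = 0.2 points
- p = 0.10, d = 10: 0.10 × 10 = 1.0 point
- p = 0.30, d = 2: 0.30 × 2 = 0.6 points
- p = 0.30, d = 10: 0.30 × 10 = 3.0 points

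The number affected would be 16 × 0.10 = 1.6 to 16 × 0.30 = 4.8, or about 2 to 5 of 16 subjects. With f = 13/16 = 0.81, the range is 0.81 × 0.2 = 0.16 to 0.81 × 3.0 = 2.4 points. If after-effects do not alter these tests, d = 0 and the shift is zero.

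**Step 5. What a fixed order achieves.** If tests come first at each visit, the previous scheduled puncture is 84 - 42 = 42 days earlier at Week 12 and 168 - 84 = 84 days earlier at Week 24. No test would then fall just after a study puncture.

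**The case against.** The strongest reply is that the consequence is small. The statistical section plans summary statistics and rules out an efficacy analysis. Without a control arm, change over 24 weeks in FVC or swallowing cannot be separated from ALS progression whatever the order. No document shows that a puncture changes these tests the next day. All of this stands, and it limits the weight of the point. It does not remove it. Section 12.3.9 still plans the within-person DIGEST comparison, section 15 assigns analysis of swallowing and respiration, and descriptive changes are exposed in the same way. Reordering will not make the changes attributable to metformin, but it removes one avoidable source of ambiguity.

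A reader might infer that puncture after-effects are built into every before-after change, in all 16 subjects, and always towards decline. The documents do not support that. ALSFRS-R has no reversal, Week 12 has no stated order, and FOIS and EAT-10 are also taken by telephone at Weeks 18, 36 and 52, when no puncture is scheduled. Section 12.2.2.5 permits testing before the puncture, and three participants may have a remote one. The existence, size and direction of any effect are assumed.

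A reader might also infer that the first dose precedes the baseline puncture and blood draw. That requires placing the synopsis's Day 1 on Table 3's calendar. Within the synopsis, puncture and imaging are described before the Day 1 return and the dose. In Table 3 and 12.2.2.1, drug is dispensed on Day 2, the puncture day, and in the text list it comes after the draw and the puncture. Neither source alone has dosing before the baseline samples. What stands is that the day labels differ.

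**Conclusion.** The point holds as an unstandardised and, in Table 3, reversed order of testing relative to the puncture. It concerns the Week 24 changes in FVC, peak cough flow, swallowing measures (VFSS with PAS and DIGEST, FOIS, EAT-10) and, through a smaller change of timing, MRI/DTI. These changes may be confounded by a recent puncture to an unknown degree. The range of 0.2 to 3 points illustrates assumed inputs and is not an estimate; zero is also possible. The schedule finding is firm for baseline. For Week 24 it depends on Table 3 being followed over the looser wording of 12.2.2.5. This does not threaten the safety objective. It should be corrected because it is cheap to prevent and cannot be removed afterwards.

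**What to change.** Set one order for Visits 1, 3 and 4 and state it in section 12.1: swallowing tests, FVC, peak cough flow and, where scheduled, MRI come before the puncture. At Week 24 this can be done in either of two ways:

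- Move the Day 2 tests and MRI to Day 1, ahead of the puncture. This makes Day 1 longer.
- Move the puncture, with its paired RAN blood draw, to after the Day 2 tests. This puts the puncture at the end of the visit, which is less convenient for those who travel, and separates it from the Day 1 safety labs. ALSFRS-R should keep the same position relative to the puncture as at baseline.

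At Visit 1 Day 2, state that MRI precedes the puncture. At Visit 3, state the order within the day. Reword 12.2.2.5 so that it gives the same order as Table 3. Record the date and time of each puncture and test, including remote punctures, so that out-of-order visits can be flagged and the summaries repeated without them.

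Separately, reconcile the synopsis with Table 3 and section 12.2.2.1 on the labelling of the baseline days, so that it is clear how the first dose and the baseline samples are sequenced.

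The cost is less freedom in booking slots. No new visit or procedure is needed.

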**CONFIDENTIAL INFORMATION**

The information in this study protocol is confidential. Any disclosure, copying or distribution of the information contained within is strictly prohibited without written consent from University of Florida.

Drug Accountability/Compliance				x	x		x		
--------------------------------	--	--	--	---	---	--	---	--	--

### Outcome Measures:

**Primary:** 1. ALSFRS-R score

**Secondary:** 2. Soluble GP in blood; 3. Swallowing physiology (PAS, DIGEST); 4. PFT's (FVC, PCF); 5. MRI/DTI outcomes.

## 12.2. Timing of Study Activities

No study procedures will be performed prior to the signing of the Informed Consent Form (ICF). All subjects will sign an ICF prior to undergoing any study tests or procedures.

Visit windows are consecutive calendar days and the target visit dates are calculated from the Baseline Visit, which should occur within 14 to 28 days of the Screening Visit. All clinic visits and calls after the Baseline visit will have a +/- 7 work day window.

Inclusion in the study is entirely voluntary and subjects may withdraw at any time for any reason. Possible reasons for withdrawal could include serious adverse events, adverse events, and subject's choice. Subjects wishing to stop medication will immediately discontinue test article. Subjects who elect to discontinue medication will be asked to comply with end of study assessments (visit 4 on Table 3 Schedule of Activities) at a follow up visit in an outpatient setting (to be determined by Investigator or Staff) at 14 +/- days after the last treatment dose. Subjects who withdraw due to an adverse event will be followed whenever possible until resolution of the adverse event. It may be appropriate for the subject to return to the site 2 weeks after the subject is off study to evaluate for resolution of any adverse events and to receive further information about options for future clinical care. The Investigator will decide the course of action.

### 12.2.1. Screening procedures

At the screening visit, potential subjects will be informed about study procedures and will then sign an informed consent form. Inclusion/exclusion criteria will be reviewed and a medical history and comprehensive physical and neurological examination will be completed. Vital signs, height, weight, and concomitant medications will be recorded. Safety laboratory tests will be performed including complete blood count (CBC) with differential, electrolytes, BUN, creatinine, ALT, AST, total bilirubin, albumin, and a urine pregnancy test for women of childbearing potential. and COVID-19 nasal collection and testing.

The following procedures will be performed during the screening visit:

- Informed consent
- Inclusion/exclusion assessment

---

#### CONFIDENTIAL INFORMATION

The information in this study protocol is confidential. Any disclosure, copying or distribution of the information contained within is strictly prohibited without written consent from University of Florida.

- Documentation of Disease
- Medical history/Demographics
- Record concomitant medications
- Clinical labs for safety (hematology, chemistry, liver functions, and urinalysis)
- C9+ and RAN protein blood draw
- Urine Pregnancy Test (females of childbearing potential)
- COVID-19 nasal collection and testing - Due to COVID-19 Pandemic nasal collection and testing of the participants has been implemented to determine if the participant is COVID negative. The collection is done at UF Springhill collection site and testing is completed at Rocky Point Labs overnight with results placed in EPIC. The results of the testing will be provided to the participant once results are posted in EPIC. This will collection and testing will continue throughout the participants participation in the study at this visit.
- Vital signs
- Height and weight
- Comprehensive physical and neurological examinations
- ALS Functional Rating Scale – Revised (ALSFRS-R)
- BDI-Fast Screen

As part of the screening visit, the investigator will determine the competence of caregiver to administer the study drug at home. Teaching will begin on the importance of compliance and proper handling of study drug. All inclusion and exclusion criteria and safety laboratory tests will be reviewed by the investigator prior to scheduling the baseline visit (visit 1 on schedule of activities table). A paper log will be kept at the site to record all subjects screened for entry into the study. This information will also be captured electronically in the electronic data capture system (EDC) using REDCap. REDCap (Research Electronic Data Capture) is a secure, Web-based application designed to support traditional case report form data capture. Demographic characteristics of all subjects who are screened will be recorded whether or not they qualify for entry into the study. The reason for non-qualification will be recorded for all subjects who are not eligible. The reason for nonparticipation will also be recorded for subjects who are eligible but choose not to participate in the trial. If a subject fails screening for the study, the subject can be re-screened if the investigator determines it is appropriate to do so. At any time during the study, repeat laboratory tests can be obtained if the investigator or central laboratory believes that a laboratory test result is in error. Additional laboratory tests may also be obtained at any time during the study, at the discretion of the investigator.

